primarily to genotype – a known confounder (41). The American College of Sports Medicine’s classifications of training status (i.e., <150 minutes of moderate-intensity and/or <75 minutes of vigorous aerobic exercise per week for the last 3 months) as well as normative $\text{VO}_{2\text{max}}$ values will be used to dichotomize the groups with the fit (and chronically-trained) and unfit (and sedentary) group having values in the upper and lower quartiles (i.e., $\geq 75^{\text{th}}$ percentile and $\leq 25^{\text{th}}$ percentile) for their age and sex, respectively (42). This equates to a $\text{VO}_{2\text{max}}$ value of ≥ 55.2 and 44.7 ml/kg/min for fit males and females, respectively, and ≤ 40.1 and 30.5 ml/kg/min for unfit males and females, respectively. Participants will then be provided with a wearable, wrist-worn sleep and cardio-autonomic function monitor, to be worn on the non-dominant wrist throughout the entirety of the project timeline, including a two-week initialization period to establish baseline sleep cardio-autonomic data. This initialization period will take place following consent and prior to the first data collection visit. Next, participants will then be familiarized with daily sleep, physical activity, and 3-day nutrition logs as well as a PVT smart phone application, all of which will be performed throughout the study. Lastly, participants will be assessed for sleep chronotype via a morningness-eveningness questionnaire to inform any potential differences in sleep intervention response post hoc. Following the initialization period, participants will be randomly assigned to either a normal or partial sleep deprivation intervention, both of which will last 4 days. The partial sleep deprivation intervention will consist of prescribed bed and wake times eliciting a 30% reduction in habitual time in bed, identical to a protocol utilized by Roberts, et al. (43). Following the first sleep intervention period, participants will again report to the ISSM for the first of four data collection visits (i.e., Post-Test 1). Data collection will consist of assessment of central hemodynamics, cardio-autonomic function, physical and cognitive performance, as well as overall health. Participants will then undergo a 7-day washout/ post-intervention observation period, in which they will continue to track and log their sleep and perform daily PVT to allow for recovery evaluation in those metrics, prior to crossing over to the other sleep intervention. During the washout period, participants will also return to the lab to repeat the blood work and CMJ testing to allow for recovery assessment in those values (i.e., immediate post-intervention vs 3-day post-intervention values; Recovery 1). Following completion of the washout/observation period, participants will crossover to the other sleep intervention and repeat the testing protocols (i.e., Post-Test and Recovery 2). Data collection visits will occur at the same approximate time of day for each individual to account for diurnal patterns in the data collected. In total, the protocol will last approximately 5 weeks and consist of 5 visits.

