
6.2 Research Procedures

Initial Visit: All data collection time points are outlined in Figure 1 below. Prior to participation, voluntary consent to participate will be obtained. Eligible participants (i.e., those deemed fit to participate via the Physical Activity Readiness Questionnaire [PAR-Q+] in conjunction with the American College of Sports Medicine guidelines for physical activity) will then complete a questionnaire to establish typical training characteristics (i.e., frequency, intensity, time, type, and history). Specifically, the PAR-Q+ screens individuals for signs or symptoms of cardiovascular, metabolic, and or renal disease which would make it inadvisable for them to participate in physical activity. Individuals who are not deemed fit to participate, according to the PAR-Q+, will not be allowed to continue with participation. They will then be assessed for body composition (Bod Pod; Cosmed, Chicago, IL) prior to performing a maximal treadmill test (protocol described below) to determine maximal oxygen consumption capacity (VO_{2max}). In the case that an individual does not qualify for the study (i.e., those meeting requirements for training status and VO_{2max}), all data collected on that individual will be destroyed. Individuals who do qualify will be provided with a WHOOP (Boston, MA) wearable, wrist-worn multi-sensory biometric and cardio-autonomic function monitor. The WHOOP band will be worn on the non-dominant wrist throughout the entirety of the project timeline (~1.5 months), including a two-week initialization period prior to the first data collection visit. Participants will then be familiarized with daily sleep, physical activity, and 3-day nutrition logs as well as a PVT smart phone application, all of which will be performed throughout the study. Specifically, participants will complete the sleep and physical activity logs and PVT task daily throughout the enrollment period, while they will complete the 3-day nutrition log in the 3 days immediately prior to Post Test 1 and 2 visits (described in detail below). Lastly, participants will be assessed for sleep chronotype via a morningness-eveningness questionnaire to inform any potential differences in sleep intervention response post hoc.

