16.2 N/A

17.0 Data Management and Confidentiality

17.1

Sample Size Estimation

Sample size requirements were determined via a priori power analyses using G*Power software (Ver. 3.1.9.4; Heinrich-Heine-Universität Düsseldorf, Düsseldorf, Germany) to ensure sufficient statistical power. To inform the expected effect size, we referenced Sunbul, et al. (49) who reported significantly higher wave velocity (PWV) values (5.33 ± 0.46 m/s) following one night of total sleep deprivation compared to one night of normal sleep (5.15 ± 0.26 m/s; $p=0.001$) in young, healthy males and females. Acknowledging that this will consist of an acute partial sleep deprivation intervention, a Cohen's f value of 0.24 was used in conjunction with an α level of 0.05, power of 0.80, with 2 groups (crossover design; 4 measures each), and a conservative correlation among repeated measured of 0.5. This resulted in a sample size estimate of 24 participants. The planned sample size was then increased based on the differences between the current study, the previous work, and the assessment of several secondary outcomes, as well as to account for expected attrition (~20%). Therefore, 30 participants will be recruited to maximize statistical power and account for expected attrition.

Statistics

Data will be presented as means \pm SD if normally distributed and assessed for normality via a Shapiro-Wilk Test. Assuming normality, all variables will undergo null-hypothesis testing with the α level set to 0.05. In the case that normality is violated, the appropriate non-parametric alternatives will be utilized. Analyses will be conducted using SPSS version 29.0 (SPSS, Inc., Chicago, IL).

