Analysis of Variance: Central hemodynamic and arterial stiffness variables will be interpreted using a mixed-model (i.e., within-between) repeated measures analysis of variance (RMANOVA) to identify interactions between multiple groups and conditions. Specifically, to test the hypothesis that individuals with higher CRF would demonstrate a blunted arterial stiffness response (i.e., maintained pulse transit times) to the acute partial sleep deprivation intervention, cf-PWV will be assessed following 4 consecutive nights of both normal sleep and restricted sleep and compared between the two groups. Likewise, all secondary variables will be assessed at pre-specified time points using a within-between interaction RMANOVA to test the hypotheses that individuals with higher CRF would demonstrate a blunted effect of partial sleep deprivation on markers of physical and cognitive performance (i.e., maintained RSI and PVT, respectively) as well as on markers of overall health (i.e., maintained cardio-autonomic function parameters, pro- and anti-inflammatory serum cytokine levels, and mood states).

In the case that sphericity is violated, a Greenhouse-Geisser correction will be performed. In the case of significance, a post hoc one-way ANOVA with Bonferroni tests will be used to identify significant differences. Effect sizes (ES) will be calculated by standardizing mean differences to the standard deviations (SD) of the placebo condition. Effect sizes will be qualified as follows: small $d = 0.2$, moderate $d = 0.5$, and large $d \geq 0.8$ (50).

17.2 The data will be kept secure through several routes. First, only the CITI certified research team will be allowed to be involved in the data collection process. Further, after acute bouts of data collection occur, all data will be collected together by the PI. If the data is physical, it will be kept in a locked drawer, behind a locked laboratory door. If the data is electronic, it will be kept on a password secured computer that only the PI may gain access. All human data will be coded, such that without the code it becomes unidentifiable.

17.3 Quality control of collected data will be ensured by controlling as many external variables as is reasonable. Further, biological measures (primary outcomes) will be measured in duplicate with the average of each measure used in the final assessment.

17.4 Describe how data or specimens will be handled study-wide:

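### Daily WHOOP and PVT values exist before both sleep blocks, but the secondary analysis gives them no role and names no period or order term, so it may forgo precision and some drift control

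*Combined protocol and SAP*

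**What the plan says.** Section 6.1 has the WHOOP band worn for the whole project, "including a two-week initialization period to establish baseline sleep cardio-autonomic data". Section 6.2 (Initial Visit) adds that "participants will complete the sleep and physical activity logs and PVT task daily throughout the enrollment period". Sleep tracking and the daily PVT continue through the 7-day washout, where their stated purpose is to evaluate recovery. WHOOP and PVT values are therefore available just before block 1 (run-in) and just before block 2 (washout).

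Only the WHOOP run-in is described as a baseline. The one concrete use given for the last run-in week is to characterize habitual sleep, from which bed and wake times are prescribed.

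For analysis, section 17.1 states that "all secondary variables will be assessed at pre-specified time points using a within-between interaction RMANOVA". It does not list the time points. It names no baseline covariate, change score, period term or sequence term. The assessment paragraphs of section 6.2 speak of response, recovery and changes in response time, but define no reference window.

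**The concern.** With two conditions and two fitness groups, the group-by-condition interaction is a comparison between groups of each person's restricted-minus-normal difference. Fixed differences between people cancel in it. Change within a person between the blocks does not. The blocks start 11 days apart (4 intervention days plus 7 washout days), or further apart if a block is restarted. Practice on a daily PVT, a change in training load, or illness could all move a person's level in that time. Training load matters here because the groups are defined partly by training status.

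Such drift stays in the error term of the interaction. An order term removes a shift common to everyone, and none is named. A person's own pre-block value can remove part of the person-specific shift. At stake is precision for the autonomic part of Aim 2 and the cognitive part of Aim 3, with 15 people per group if 30 split evenly.

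**Working it through.** **1. The plan's own figure.** Section 17.1 gives an "f value of 0.24 was used in conjunction with" alpha 0.05 and power 0.80, "with 2 groups (crossover design; 4 measures each", and a "conservative correlation among repeated measured of 0.5". It concludes: "This resulted in a sample size estimate of 24 participants".

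For the within-between interaction, λ = f²·N·m/(1−r), with df (m−1) and (N−2)(m−1), taking sphericity.
- N = 24, m = 4: λ = 0.0576 × 24 × 4/0.5 = 11.06, df 3 and 66, power 78.0%.
- The smallest even N reaching 80% is 26 (81.7%). The stated 24 is reproduced to within 2 participants, and 24/(1 − 0.20) = 30.

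**2. Reference case.** Two conditions (m = 2), N = 30: λ = 0.0576 × 30 × 2/0.5 = 6.912, df 1 and 28, power 71.8%. Applying f = 0.24, chosen for PWV, to WHOOP and PVT outcomes is an assumption.

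**3. What a baseline can add.** Let D be the restricted-minus-normal difference, E the matching difference of the two pre-block baselines, and q = corr(D, E).
- Covariate: Var(D adjusted for E) = Var(D)·(1 − q²), at a cost of 1 df.
- Change score, equal variances: Var(D − E) = Var(D)·(2 − 2q).

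| q | Covariate: variance ratio | Power | Change score: variance ratio | Power |
|---|---|---|---|---|
| 0 | 1.00 | 71.7% | 2.00 | 43.5% |
| 0.2 | 0.96 | 73.5% | 1.60 | 51.9% |
| 0.4 | 0.84 | 79.0% | 1.20 | 64.0% |
| 0.6 | 0.64 | 88.6% | 0.80 | 81.0% |

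If all four measures share one correlation of 0.5, Cov(D, E) = 2(0.5 − 0.5) = 0, so q = 0 and the gain is nil. Change scores lose power whenever q is below 0.5.

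**4. A plausible range for q².** The documents give no day-to-day correlations, so this step is assumption. Take a daily series of variance 1: a slow component with share s and day-to-day correlation φ, plus independent noise. The baseline is a 3-day mean, the outcome the following 4-day mean, and block starts are 11 days apart.

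Worked cell, φ = 0.9, s = 0.6 (φ¹¹ = 0.314):
- 4-day mean: variance 0.6 × 14.098/16 + 0.4/4 = 0.629; covariance 11 days apart 0.6 × 0.314 × 16.223/16 = 0.191. Var(D) = 2(0.629 − 0.191) = 0.876.
- 3-day mean: variance 0.6 × 8.22/9 + 0.4/3 = 0.681; covariance 0.6 × 0.314 × 9.067/9 = 0.190. Var(E) = 2(0.681 − 0.190) = 0.983.
- Baseline with its own block: 0.6 × 8.388/12 = 0.419. First baseline with second block: 0.419 × φ¹¹ = 0.132. Second baseline with first block: 0.419 × φ⁴ = 0.275. Cov(D, E) = 2 × 0.419 − 0.132 − 0.275 = 0.432.
- q² = 0.432²/(0.876 × 0.983) = 0.22.

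Over φ = 0.8-0.95 and s = 0.2-0.6, q² is 0.03-0.22. With person-specific drift of 0.04 SD per day it is 0.13-0.33. At φ = 0.5, s = 0.2 it is about 0.01. Across all these settings the change-score variance ratio is 0.90-2.1.

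**5. Simulation.** 15 per group, interaction of 0.8 daily within-person SD, order term in both models.
- φ = 0.9, s = 0.6: power about 61-62% unadjusted, 70-71% adjusted.
- With person-specific drift: about 57-59%, rising to 66-69%.
- φ = 0.5, s = 0.2: about 77-78%, falling to 75-76%.
- Type I error of the adjusted test: 4.6-5.8%.

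**6. Bias checks.**
- With an assumed group-specific drift of 0.5 SD and order splits of 8/7 and 11/4, adjustment reduced bias from −0.14 to −0.09.
- An assumed group-specific residual effect of 0.3 SD in the late washout moved the adjusted estimate by 0.01-0.07 SD, with no visible inflation of type I error.

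**The case against.** A reader might infer that all these data are collected expressly as baselines, that the plan then discards them, and that power is certainly lost. The documents do not support that.
- The baseline purpose is stated only for the WHOOP run-in. The daily PVT has none, and the washout days serve recovery evaluation.
- The secondary time points are unlisted, and section 6.2 refers the WHOOP and PVT methods to cited studies. The plan is silent on pre-block values; it does not exclude them.
- The only correlation in the plan, a common 0.5, implies no gain.

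All three points stand. The third has limited force: that value was an input to a PWV-based calculation, and for a daily series it implies that the days just before a block predict its outcome no better than days from the other period.

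Three further objections carry weight. A crossover RMANOVA without period baselines is valid. Random order balances common drift on average, so bias needs both group-specific drift and uneven order, and even then adjustment leaves about two thirds of it (0.09/0.14). The late-washout baseline follows block 1 and may carry residual effects that differ by fitness group. Restarted blocks also need a rule, or failed restricted nights could enter the baseline. These limit the claim and shape the fix; they do not give the pre-block data a role.

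**Conclusion.** The point holds as an optional refinement. Section 17.1 assigns no role to WHOOP and PVT values available before both blocks and names no period or order term, so it may forgo precision and some control of within-person drift for four secondary outcomes.

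The size rests on assumed correlations: nil under a common 0.5; about 3-22% of the variance of the condition difference when the slow component holds 20-60% of the variance with day-to-day correlation 0.8-0.95; and a loss of about 2-3 power points when there is almost no day-to-day correlation. Nothing here shows the planned test to be invalid or biased under balanced order. The primary outcome is not touched.

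**What to change.** For heart rate variability, resting heart rate, recovery score and PVT only, state before analysis:

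1. The outcome time points, and a pre-block baseline equal to the mean of the last 3 days before each block (run-in days 12-14; washout days 5-7). Where a block was restarted, use the 3 days before the first attempt.
2. The test: fitness-group effect on each person's restricted-minus-normal difference, with the matching baseline difference and block order as covariates. Do not subtract the baseline as a change score.
3. The adjusted analysis is the main one and the unadjusted one a sensitivity analysis, so that the result cannot be chosen afterwards.

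The analysis of cf-PWV, blood markers, POMS and RSI stays as planned.

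Cost: wording only, with no new data or visits. The baseline covariate uses one degree of freedom per outcome. Residual effects of the first block may enter the late-washout covariate; the unadjusted analysis lets readers judge this.

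### The primary cf-PWV interaction test relies on equal response variance in the fit and unfit groups, which the plan neither checks nor relaxes; the sphericity rule it does state cannot act on a two-condition test

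*Combined protocol and SAP*

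**What the plan says.** Section 17.1 (Analysis of Variance) assigns the central hemodynamic variables to a within-between repeated-measures ANOVA. For the arterial stiffness hypothesis it names cf-PWV, measured after each of the two sleep conditions and compared between the fitness groups.

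Three provisions govern assumptions:
- Sphericity: "In the case that sphericity is violated, a Greenhouse-Geisser correction will be performed".
- Normality: data are "assessed for normality via a Shapiro-Wilk Test", with unnamed non-parametric alternatives if the check fails. The text does not say whether raw values, differences or residuals are tested.
- Error rate: "all variables will undergo null-hypothesis testing with the α level set to 0.05".

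Nothing is said about equal variance between the fitness groups, and no heteroscedastic version of the test is offered.

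The groups are selected, not randomised. Section 6.1 forms them from self-reported training status and the upper and lower VO2max quartiles. No group sizes or quotas are given. Section 12.2 allows up to 36 recruits for 30 completers, and section 14.1 withdraws participants who do not keep to the prescribed bed and wake times.

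The number of cf-PWV measurements is not consistent. The analysis text describes two. The sample size text has "with 2 groups (crossover design; 4 measures each". Section 6.2 (Central Hemodynamic Assessment) adds a repeat three days after each intervention, but section 6.2 (Experimental Visits) lists only blood work and jump testing at the recovery visit.

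**The concern.** With two conditions and two groups, the interaction F is the square of a pooled-variance t statistic on the within-person differences. The plan guards against a failure that cannot occur in this test and is silent on the one that can.

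If the variances of the differences are unequal and the group sizes are unequal too, the pooled standard error is wrong. When the smaller group is the more variable one, p-values are too small and confidence intervals too narrow. In the reverse case the test is conservative. Groups taken from opposite ends of the fitness distribution give no design-based reason to expect equal response variance.

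**Working it through.** **The plan's own figure.** The source SDs are 0.46 and 0.26 m/s and the mean difference is 5.33 − 5.15 = 0.18 m/s.
- d = 0.18/√((0.46² + 0.26²)/2) = 0.482, and f = d/2 = 0.241. This agrees with "a Cohen's f value of 0.24 was used in conjunction with an α level of 0.05, power of 0.80".
- Within-between interaction with λ = f²·N·m/(1 − ρ), m = 4 and "a conservative correlation among repeated measured of 0.5": power is 78.0% at N = 24 and 81.7% at N = 26. The statement "This resulted in a sample size estimate of 24 participants" is reproduced to within two participants.

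**Sphericity.** With m = 2 there is one within-person contrast, so the Greenhouse-Geisser epsilon is exactly 1. It is also inert in a 2×2 condition-by-time layout, where each within-person effect has 1 df. It acts only if four occasions are treated as one four-level factor.

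**An SD ratio to work with (assumed).** Suppose unfit participants had the source SDs in the two conditions, fit participants kept 0.26 in both, and the within-person correlation were 0.5.
- Unfit: √(0.46² + 0.26² − 2·0.5·0.46·0.26) = 0.3995.
- Fit: 0.26·√(2(1 − 0.5)) = 0.26.
- Ratio: 0.3995/0.26 = 1.54. Under the same construction it is 1.44 at correlation 0 and 1.80 at 0.8.

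**True size of the pooled test.** Take the fit SD as 1, so the unfit variance is 1.54² ≈ 2.36 (unrounded ratio 1.5365). For 18 fit/12 unfit:
- Pooled variance expected: (11·2.361 + 17·1)/28 = 1.535.
- Squared SE used: 1.535·(1/12 + 1/18) = 0.213.
- True squared SE: 2.361/12 + 1/18 = 0.252.
- SE used/true SE: √(0.213/0.252) = 0.92.
- The critical value 2.048 then acts like 2.048·0.919 = 1.882, whose two-sided t tail on 28 df is about 7.0%.

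Averaging over the sampling distribution of the variances (normal differences, equal mean responses, no period effect) gives:

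| Fit/unfit | Pooled, ratio 1.5 | Pooled, ratio 1.54 | Welch |
|---|---|---|---|
| 15/15 | 5.1% | 5.1% | 5.0% |
| 16/14 | 5.7% | 5.8% | 5.0% |
| 18/12 | 7.1% | 7.2% | 5.0% |
| 20/10 | 8.6% | 8.8% | 5.1–5.2% |
| 12/18 | 3.6% | 3.5% | 4.9–5.0% |
| 10/20 | 2.7% | 2.6% | 4.9–5.0% |

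Coverage of the pooled 95% CI is 100% minus these figures: 92.8% at 18/12 and 96.5% at 12/18 for ratio 1.54.

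**How 18/12 could arise.** If 18 per group start and all six allowed losses are unfit, 18 fit and 12 unfit complete. This is an illustration, not a forecast.

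**Normality target.** In a simulated sample of 30 with skewed person effects and normal errors, Shapiro-Wilk rejects raw values 72% of the time and the differences 5%. With normal person effects and a skewed response, it rejects raw values 5% of the time and the differences 97%. The shapes are invented; they show only that the tested quantity decides the outcome.

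**Power cost of Welch when variances are equal.** With f = 0.24, m = 2, ρ = 0.5 and N = 30, λ = 0.0576·30·2/0.5 = 6.912. In SD units of the difference, d = √6.912/√(15·15/30) = 0.96. Power falls from 71.8% to 71.6% at 15/15, and from about 70% to about 69% at 18/12.

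**The case against.** Four counter-arguments have weight.

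1. **The SDs are not group SDs.** A reader might infer that the plan's own figures show unequal variances between fitness groups. They do not. The SDs 0.46 and 0.26 m/s belong to two conditions in one cited sample, "one night of total sleep deprivation compared to one night of normal sleep". Carrying them to fitness groups requires assuming that a smaller mean response is also a less variable one, and that total deprivation stands in for partial. This stands, so the ratio is a scenario only.

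2. **The scenario borrows from the alternative.** A type I error presupposes equal mean responses, while the 1.54 ratio was built from one group responding and one not. This stands as a criticism of that derivation. It does not remove the issue: differently selected groups can differ in response variance for other reasons, and interval coverage is affected whatever the true mean difference.

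3. **Group sizes may be nearly equal.** A reader might infer that the error rate is 3% to 9%. That range needs splits such as 12/18 up to 2:1, which the documents neither state nor predict. At 15/15 the size is practically nominal.

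4. **The Greenhouse-Geisser sentence is not an error.** It follows text that also covers secondary outcomes, some measured at four visits or daily, where it is appropriate. On a two-level factor it changes nothing. If cf-PWV were analysed as one four-level factor, it would apply there too.

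A reader might also infer that normality is checked on raw values, so that sound data would often be diverted to another test. Section 17.1 does not say that; the target is unspecified.

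**Conclusion.** The point holds in limited form. For the two-condition cf-PWV comparison in section 17.1, the stated sphericity rule is inert, and equal variance of the within-person differences between the fitness groups is assumed without comment.

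The consequence depends on two things the documents do not give: the ratio of the SDs of the differences and the group sizes at analysis. With a ratio near 1.5, the size error is about 0.1 point at 15/15, under 1 point at 16 fit/14 unfit, about +2 points at 18/12 and about −1.5 points at 12/18. The calculation also assumes normal differences and no period or sequence effect.

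The case for acting is that protection can be specified in advance at almost no cost. It does not rest on evidence that the test will be invalid. The unspecified normality target is a separate, smaller gap in the same section.

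**What to change.** In section 17.1:

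- Make the primary test a Welch t-test, with 95% CI, comparing the within-person restricted-minus-normal cf-PWV difference between fitness groups. Alternatively, use a mixed model with group-specific variances. The model can also carry a period term, which a plain Welch test on the differences omits.
- State that normality is assessed on those differences, by group, or on the model residuals, and name the non-parametric alternative. A rank test is not a remedy for unequal variances: a Mann-Whitney test on normal differences had a size of about 6% at 18 fit/12 unfit with ratio 1.5.
- Keep Greenhouse-Geisser for outcomes with three or more repeated levels.
- Reconcile section 6.2 (Experimental Visits and Central Hemodynamic Assessment) with both parts of section 17.1 on whether cf-PWV is measured two or four times. If four, define the within-person factor or factors.
- State the target size of each fitness group. Near-equal groups remove most of the problem.

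The cost is analysis-plan wording and under 1 point of power if the variances are in fact equal. No extra data are needed for the change of test.

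### The follow-up to a significant RMANOVA is an ordinary one-way ANOVA with no stated factor, error term or Bonferroni family; applied to restricted versus normal sleep it ignores the within-person pairing

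*Combined protocol and SAP*

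**What the plan says.** Section 17.1, under Analysis of Variance, tests the hypotheses with a "mixed-model (i.e., within-between) repeated measures analysis of variance (RMANOVA) to identify interactions between multiple groups and conditions". For arterial stiffness, "cf-PWV will be assessed following 4 consecutive nights of both normal sleep and restricted sleep and compared between the two groups". So each participant supplies a value under both sleep conditions, and fitness group is the only between-person factor.

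If the result is significant, "a post hoc one-way ANOVA with Bonferroni tests will be used to identify significant differences". Nothing further is said about which means are compared, which error term is used, or how many comparisons Bonferroni divides by.

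Two other sentences in 17.1 bear on the same step. On distributional failure: "In the case that normality is violated, the appropriate non-parametric alternatives will be utilized". No test is named. On effect sizes: they are obtained by "standardizing mean differences to the standard deviations (SD) of the placebo condition". The study summary lists only two conditions, a 30% and a 0% restriction of sleep.

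**The concern.** The hypotheses in section 2.0 are that fitter people respond less to restricted sleep. Once the interaction is significant, the natural next question is whether each group changed between normal and restricted sleep, and by how much. That is a comparison of people with themselves. An ordinary one-way ANOVA uses an error term that still contains the stable differences between people, which the crossover was meant to remove. The plan labels its within-person models as repeated measures and omits that label here, so the plain reading is the ordinary version.

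At stake is the description of the interaction. A real change in the unfit group could be reported as non-significant directly after a significant interaction, leaving a blunted response poorly characterised.

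The fallback raises a related issue for markers that are often skewed, such as CRP and the cytokines of Aim 2. Wilcoxon, Friedman, Mann-Whitney or Kruskal-Wallis tests on the raw values compare conditions or groups. They do not test group by condition. With no test named, the choice is left until the data are seen.

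**Working it through.** **Inputs from section 17.1.** Cohen's f 0.24; alpha 0.05; power 0.80; 2 groups; 4 measures; correlation 0.5; cited PWV 5.33 ± 0.46 m/s after sleep deprivation and 5.15 ± 0.26 m/s after normal sleep, a difference of 0.18 m/s; planned sample 30.

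**Assumptions.** 15 per group (the split is not stated). The cited SDs and difference are carried over to this trial, although they come from one night of total deprivation.

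**The plan's own figure.** For the within-between interaction, λ = f²·N·m/(1 − r), with 3 and 3(N − 2) degrees of freedom.
- N = 24: λ = 0.0576 × 24 × 4 / 0.5 = 11.06; power 0.780.
- N = 26: λ = 11.98; power 0.817.

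The stated 24 is therefore reproduced to within two participants, and 24/(1 − 0.20) = 30 matches the planned number. This calculation concerns the RMANOVA, which uses the correlation of 0.5. The post hoc step, read as an ordinary one-way ANOVA on condition, does not.

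**Standard error of restricted minus normal, one group of n = 15.**
- Paired: √[(s₁² + s₂² − 2·r·s₁·s₂)/n]
- One-way on two conditions: √[(s₁² + s₂²)/n]

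*Cited SDs, 0.26 and 0.46.* s₁² + s₂² = 0.0676 + 0.2116 = 0.2792. The covariance term is 2 × 0.5 × 0.26 × 0.46 = 0.1196.
- Paired: √(0.1596/15) = 0.103
- One-way: √(0.2792/15) = 0.136
- Ratio: √(0.2792/0.1596) = 1.32

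*Common SD.* √(0.2792/2) = 0.374, so the difference is 0.18/0.374 = 0.48 SD.
- Ratio: 1/√(1 − r) = 1/√0.5 = 1.41

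**Power and type I error by simulation** (n = 15, r = 0.5, difference 0.18 m/s, two-sided):

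| | Paired | One-way on condition |
|---|---|---|
| Power at 0.05, cited SDs | 37% | 20% |
| Power at 0.05, common SD | 41% | 18% |
| Power at 0.025 (Bonferroni for two), cited SDs | 26% | 11% |
| Power at 0.025, common SD | 29% | 10% |
| Type I error at nominal 0.05, cited SDs | 5.1% | 1.4% |
| Type I error at nominal 0.05, common SD | 4.9% | 0.8% |

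**Sensitivity to the correlation.** At r = 0.7 the ratio is 1.58 with the cited SDs and 1.83 with a common SD. With a common SD it is 1.20 at r = 0.3.

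**Where the one-way test is sound.** In a simulated four-cell one-way ANOVA (15 per group, no true differences), comparing fit with unfit inside one condition kept type I error at 0.050 to 0.053. Those are different people, so no pairing is lost.

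**Whether a rank test can address the interaction.** With two conditions, the group-by-condition interaction is the between-group difference in each person's restricted-minus-normal change. Mann-Whitney on those changes, with simulated lognormal data and 15 per group, had type I error 0.049. Its power for a shift of 1 unit was 55%, against 31% for a t-test on the same changes.

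**The case against.** The strongest reply is that the plan never says the one-way ANOVA is applied to sleep condition. It could compare fit with unfit within a condition, or be a one-way repeated-measures ANOVA, and both would be valid. That stands, and the figures above apply to one reading only. However, comparing the two fitness groups within a condition does not show whether either group responded. Fitness also has only two levels, so Bonferroni tests suggest a larger set of cells, probably including repeated measurements; Bonferroni across separate group comparisons remains possible.

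It is also right that the hypotheses are judged by the interaction, that the RMANOVA handles the pairing, and that the follow-up runs only after significance. The power figures above are not conditional on that step. With positive correlation the fault adds no false positives.

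Three stronger readings are tempting, and the documents do not support them.
- That the non-parametric fallback cannot test the interaction, or that skewed outcomes go untested. No fallback test is named, and a rank test on within-person changes fits the existing sentence.
- That published intervals will be too wide. The plan promises means with SDs, hypothesis tests and standardised effect sizes, and no confidence intervals.
- That the primary inference is invalid. It is not touched.

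The placebo wording is a slip with an evident intended meaning.

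**Conclusion.** The concern holds as a fault in the follow-up analysis. As written, the post hoc test leaves its factor, error term and Bonferroni family open, and its plain reading is wrong for the contrast that best describes a blunted response. On that reading, roughly half the power to detect a within-group change is lost: about 37–41% becomes 18–20%. The standard error is 1.32 to 1.41 times too large and the type I error is about 1%. These sizes rest on 15 per group, a correlation of 0.5, and a difference and SDs borrowed from total sleep deprivation. The direction needs only a positive correlation.

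The fallback and the effect-size denominator are secondary clarifications. The first should be pre-specified because common rank tests on raw values would change the question. The second names a condition that the trial does not contain.

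**What to change.** In section 17.1:

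1. Replace the one-way ANOVA with contrasts from the fitted RMANOVA or an equivalent mixed model: restricted minus normal sleep within each fitness group (paired, Bonferroni for two), and the between-group difference in that change. Report each with a 95% confidence interval.
2. Where normality fails, analyse log-transformed values in the same model. If that is inadequate, apply a Mann-Whitney or permutation test to each person's restricted-minus-normal difference. This covers the two-condition post-test comparison only. The 3-day recovery measurements and the daily PVT need their own named contrasts.
3. Define the effect-size denominator as the SD of the normal-sleep condition.

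The cost is a few sentences, ideally settled before analysis. No added visits, participants or data are needed, and the estimated means, computed differences and Mann-Whitney test are available in SPSS, the package already planned.
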